## **6.7. Device Training**

[figure not shown]
Physicians will be trained in the use of the Envi™-SR before any patient procedures. To further assure optimal device use, participating investigators will be trained by the sponsor on proper device selection and use and given ample opportunity to fully address any technical questions that may be present. Participating centers will be selected based on volume of potential cases, research experience of study team, professional qualifications, and extent of experience with the endovascular treatment of stroke. The sponsor will provide hands-on flow model testing with each investigator delegated for device use / deployment prior to the site being released to enroll patients to the study.

## 6.8. Study Procedures

### 6.8.1. Study Flow

Subjects presenting with acute ischemic stroke will be evaluated by the physician, in accordance with their institutional practice, to establish an appropriate treatment plan based on the Subject's medical condition and available diagnostic screening procedures prior to recruitment in the NV-001 Study. A representative overview of the study flow is shown in Figure 6-1.

**Figure 6-1: Study Flow: Patient is in study from time informed consent is obtained**

### **6.8.2. Screening**

Subjects will be screened against the study inclusion/exclusion criteria to determine their initial eligibility. A member of the research team (hospital/institution personnel assigned to the NV-001 Study) should review their eligibility. All subjects screened will be documented on the Screening/Enrollment log, including the reason for non-participation for subjects who do not enroll.

#### **6.8.2.1. General Medical Evaluation**

- A physical examination and medical history.
- Blood pressure and pulse prior to randomization.
- Concomitant medication at baseline

#### **6.8.2.2. Laboratory Evaluation**

Blood and/or urine specimens for the following laboratory studies:

- Pregnancy test – (for female patients with childbearing potential. Pregnancy test to be conducted with urine or serum sample, per institutional standard of care)
- Hemoglobin, and platelet count.
- Coagulation parameters: activated partial thromboplastin time (aPPT) and international normalized ratio.
- Kidney function: creatinine or eGFR
- Serum glucose.

#### **6.8.2.3. Neurologic Evaluation**

Screening NIHSS should be recorded as performed. At screening, a pre-stroke mRS will be obtained from the subject or the subject's caretaker.

#### **6.8.2.4. Computed tomography or magnetic resonance imaging**

CT or MRI obtained prior to study enrollment will be used for baseline assessment.

#### **6.8.2.5. Baseline Angiography**

Baseline angiogram is preferred to be obtained prior to randomization to assess inclusion/exclusion criteria as well as to assess clot location. It is acceptable to perform baseline angiography after randomization.

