## 6.5. Inclusion Criteria

Study subjects must meet ALL of the inclusion criteria listed below:

- 1) Clinical signs consistent with acute ischemic stroke
- 2) Pre-stroke Modified Rankin Score  $\leq 2$
- 3) Age 18 years and no upper limit (patient must be 18 years old at time of consent.)
- 4) NIHSS  $\geq 6$  at the time of randomization
- 5) Subject is able to start treatment (defined as time of arterial puncture) within 24 hours of stroke onset or last known well and within 90 minutes from last baseline CT/ MRI.
- 6) Imaging: For strokes in the anterior circulation the following imaging criteria should also be met:
  - a) If stroke onset (as defined by the time the patient was last seen at baseline) is within 6 hours: Baseline ASPECTS  $\geq 6$  on non-contrast CT (NCCT) or DWI-MRI;
  - b) If stroke onset is within 6-24 hours, advanced imaging with either CT perfusion or DWI-MRI is required. Baseline infarct volume must be  $\leq 50$ cc for patients under 80 years old and  $\leq 20$ cc for patients 80 years or older.
- 7) Location: Angiographic confirmation of an occlusion of an ICA (including T or L occlusions), M1 or M2 MCA with eTICI flow of zero (0) – one (1).
- 8) Patients for whom IV t-PA is indicated, are treated with IV t-PA without delay.
- 9) IV t-PA, if used, is initiated within three (3) hours of stroke onset (onset time is defined as the last time when the patient was witnessed to be at baseline), with investigator verification that the subject has received/is receiving the correct IV t-PA dose for the estimated weight.
- 10) Consent: The patient or the patient's LAR has signed and dated an Informed Consent Form.
- 11) Will comply with protocol follow-up schedule.
- 12) Patient was ambulatory prior to stroke, i.e. able to walk without another person's assistance.

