#### **6.8.2.7. Randomization method**

Subjects meeting the enrollment criteria, including angiographic criteria, will be randomly assigned to a treatment group in a 1:1 ratio, Envi™-SR to Control device. Randomization will define the ITT population and the assignment will determine the treatment group for the ITT analysis. Randomization assignments will be allocated through an electronic system, each initiated study site will be issued their own unique password, at least one password per site, and multiple passwords will be assigned if more than one person is randomizing subjects. Thus, Investigators can quickly determine the randomization assignment and the treatment assignment will be documented for monitoring. Deviations in treatment from the randomized

assignment will be recorded in the *Protocol Deviation* eCRF as a protocol deviation.

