#### **6.8.2.8. Screen Failure After Randomization – Follow-up**

Subjects that have been enrolled and randomized but subsequently are found to not meet inclusion / exclusion criteria will be recorded in the Deviation eCRF as a protocol deviation. These subjects are a part of the ITT population regardless of treatment and will be followed per standard study procedures.

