### 8.2. Sample Size Considerations

The objective of this trial is to demonstrate similar performance after treatment with the Envi™-SR device compared to the expected proportion of good outcomes at 90 days in the Control arm. The expected proportion of good outcomes in the Envi™-SR arm was estimated based on earlier results with Control. A -12.5% non-inferiority margin (NIM) will be used to examine the lower bound of the 1-sided 97.5% exact binomial confidence interval of the difference (Envi™-SR minus Control) in the proportion of patients with a 90-day mRS of 0-2. The null hypothesis and alternative hypothesis are presented below.

Ho: Envi™-SR – Control  $\leq$  -12.5%

Ha: Envi™-SR – Control  $>$  -12.5%

If the lower bound of the 1-sided 97.5% exact binomial confidence interval of the difference (Envi™-SR minus Control) in the proportion of patients with a 90-day mRS of 0-2 is greater than -12.5%, then non-inferiority will be established.

The planning estimates for the Envi™-SR study considered the lower bound of the 2-sided 95% (asymptotic) confidence interval from the SWIFT PRIME study for estimation (50.5%). Sample size estimates were prepared for this parallel design study assuming a non-inferiority margin of -12.5% (Envi™-SR successes [%] minus Control successes [%]). Under the alternative hypothesis, non-inferiority would be claimed if the lower bound of the 1-sided 97.5% confidence interval of the difference is less than the non-inferiority margin of -12.5%. All planning estimates are performed for the ITT population as this is the primary population for analysis.

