### Maximum Sample Size

If the gap narrows between the 2 randomized groups to 49.5% (Control) and 50.5% (Envi™-SR), 426 total patients (ITT) will be required (type 1 error rate of 2.5%, power of 80%). A loss to follow-up rate of 5% or less is expected. Missing data will be imputed as described in section 8.2.2. As multiple imputation could dampen the signal from the subject data that is imputed, an additional 5% of subjects may be added to compensate for any potential impact, leading to a total sample size of 448 subjects (ITT).

All estimates are performed based on the ITT population. However, all enrolled subjects (i.e., consented), including enrolled screen failures, will count toward the maximum sample size of 560 patients. The rate of enrolled screen failures is not expected to exceed 25%. Therefore, the maximum sample size for enrollment will be the ITT maximum sample size plus 25%, or 560 patients.

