**Table 8.1: Unadjusted Mean and 95% Confidence Limits on the Literature Rates**

Study	N	X	Y c	VAR a	W c	W c Y c	W c 
-------	---	---	----------------	------------------	----------------	-------------------------------	-----------------------------

SWIFT PRIME	98	59	0.6020	0.0024448	409.036071	246.25641	167310.508
ESCAPE	120	64	0.5333	0.0020741	482.142857	257.142857	232461.735
REVASCAT	103	45	0.4369	0.0023885	418.669349	182.913793	175284.024
EXTEND IA	35	25	0.7143	0.0058309	171.5	122.5	29412.25
MRCLEAN	233	76	0.3262	0.0009433	1060.11876	345.789809	1123851.78
				SUM	1154.60287	2541.46703	1728320.29
					$\bar{Y}$	LCL	UCL
				C=5	0.4543	0.4154	0.4932
a The VAR term in the table is actually the standard error of the $Y_c$ .							

In Table 8.2, the test of heterogeneity is computed and the adjustment if  $Q > C-1$ .

Table 8.2: Adjusted Mean and 95% Confidence Limits on the Literature Rates							
Study	$Y_c$	$\bar{Y}$	$Y_c - \bar{Y}$	$(Y_c - \bar{Y})^2$	$W_c (Y_c - \bar{Y})^2$	$W_c^*$	$W_c^* Y_c^*$
SWIFT PRIME	0.6020	0.4543	0.1477	0.02182568	8.9275	44.7338	26.9316
ESCAPE	0.5333	0.4543	0.0790	0.00624537	3.0112	45.4881	24.2603
REVASCAT	0.4369	0.4543	-0.0174	0.00030319	0.1269	44.8467	19.5932
EXTEND IA	0.7143	0.4543	0.2600	0.06758963	11.5916	38.8492	27.7494
MRCLEAN	0.3262	0.4543	-0.1281	0.01641612	17.4030	47.9548	15.6419
				SUM $Q=$	41.0602	221.8726	114.1764
$\bar{W}=$	508.29341						
$S_W^2=$	109127.34			$D_1=$	0		
U=	1861.4188			$D_2=$	0.01990968		
				$\bar{Y}^*$	$SE(\bar{Y}^*)$	LCL	UCL
				0.5146	0.0671	0.3830	0.6462

Since  $Q > C-1$ , an adjustment was made to the mean success rate and the between study standard error has increased to 0.0671. This demonstrates that the upper and lower limits are  $0.5146 \pm 0.1315$  (1.96-0.0671). The variability between and within the five (5) studies is 0.13 (13%) and a margin of equivalence that size or smaller would be appropriate. The non-inferiority margin for this study will be set at -12.5%.

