## **12.4. Event notification**

### **12.4.1. Adverse Events (AE) and Adverse Device Effects (ADE)**

All adverse events and adverse device effects shall be recorded on sponsor-provided adverse event eCRF. The safety assessments will consist of AE from the time the ICF is signed through Day 90 for those subjects treated, and to 24 hours for those subjects identified as angiographic screen failures. Adverse events and adverse device effects shall be recorded in the form of a diagnosis, rather than providing the various signs and symptoms for a particular health condition. The investigator or investigator-appointed study personnel will complete these eCRFs. Adverse event and other reporting should be provided to the sponsor according to the timelines listed in Table 12.1.

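### Section 6.8.2.5 lets the baseline angiogram follow randomisation, so subjects without a qualifying occlusion can enter the primary ITT set and dilute the non-inferiority comparison

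*Combined protocol and SAP*

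**What the plan says.** - **Eligibility.** Inclusion criterion 7 (Section 6.5) requires "Angiographic confirmation of an occlusion of an ICA (including T or L occlusions), M1 or M2 MCA with eTICI flow" of grade 0 to 1.
- **Assignment.** Section 6.8.2.7: "Subjects meeting the enrollment criteria, including angiographic criteria, will be randomly assigned to a treatment group in a 1:1 ratio". The schedule of events (Section 6.8.10, note 6) likewise uses the baseline angiogram to verify the angiographic criteria, and puts it under screening, ahead of randomisation.
- **The exception.** Section 6.8.2.5 prefers the angiogram first, then states: "It is acceptable to perform baseline angiography after randomization".
- **Who is analysed.** For subjects found ineligible after randomisation, Section 6.8.2.8 says: "These subjects are a part of the ITT population regardless of treatment and will be followed per standard study procedures". Section 5.1.2 and the Statistics part of the synopsis make ITT the primary population.
- **Follow-up.** Section 6.8.2.8 applies standard study procedures to these subjects. Sections 5.3 and 6.8.2.6 follow consented but unrandomised subjects for at least 48 hours or to discharge, whichever is earlier. Section 12.4.1 collects adverse events through Day 90 for treated subjects "and to 24 hours for those subjects identified as angiographic screen failures".

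**The concern.** A site that follows Section 6.8.2.5 cannot also satisfy Section 6.8.2.7, because criterion 7 is not fully verified at assignment. Some vessels may be open on the first run: Section 6.10.2 lets the investigator start revascularisation within 60 minutes of lysis instead of waiting to see whether it works.

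A subject with no qualifying occlusion who gets no device pass has the same expected outcome in either arm. Each such subject moves the ITT difference towards zero. When the new device is truly worse, that is the wrong direction for a non-inferiority test. The study objective (Section 3) is to compare the devices, and these subjects carry little or no information on that.

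The document defines a per-protocol set that would exclude them (Section 5.1.3). However, it does not make that set co-primary or require it to agree with ITT, and it describes no analysis restricted to confirmed occlusions. Methods 2 and 3 in Section 8.3.1 re-score only subjects who had additional therapy, so they leave an open-vessel subject untouched.

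**Working it through.** **Inputs from the protocol.** Margin: "The non-inferiority margin for this study will be set at -12.5" per cent (Section 8.2.1). Decision rule: the "lower bound of the 1-sided 97.5% exact binomial confidence interval of the difference" (Section 8.2). Planning values: "type 1 error rate of 2.5%, power of 80" per cent, stated for the 426 figure and taken here to apply to the 270 figure too. Rates are 46% v 50.5% for the target size and 49.5% v 50.5% for the maximum. Allocation is 1:1.

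**Step 1: reproduce the plan's sample sizes.** With unpooled variance, n per arm = (1.960 + 0.842)² × [pC(1−pC) + pT(1−pT)] / (pT − pC + 0.125)².

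- Target: 7.849 × 0.498375 / 0.170² = 135.4, so 136 per arm and 272 in total (plan: 270).
- Maximum: 7.849 × 0.49995 / 0.135² = 215.3, so 216 per arm and 432 in total (plan: 426).

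The Farrington–Manning constrained-variance formula gives exactly 270 and 426. The plan's figures stand.

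**Step 2: dilution model.** Let f be the share of ITT subjects with no qualifying occlusion and no device effect. Let g be their common good-outcome rate. Set Control at 46% and Envi-SR at 33.5% among subjects with a qualifying occlusion, so that the true deficit equals the margin. Then:

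- pC = 0.46(1−f) + gf and pT = 0.335(1−f) + gf
- ITT difference = −0.125(1−f)
- SE = √{[pC(1−pC) + pT(1−pT)]/n}
- P(claim non-inferiority) = Φ(0.125f/SE − 1.960)

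Example with f = 5%, n = 135, g = 46%: pC = 0.46, pT = 0.34125 and SE = 0.0592. Then 0.00625/0.0592 − 1.960 = −1.854, and Φ = 3.2%.

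| f (assumed) | ITT deficit, points | 135 per arm | 224 per arm |
|---|---|---|---|
| 0% | 12.5 | 2.5% | 2.5% |
| 1% | 12.4 | 2.6% | 2.7% |
| 3% | 12.1 | 2.9% | 3.0% |
| 5% | 11.9 | 3.2% | 3.4% |
| 10% | 11.25 | 4.0% | 4.5–4.6% |

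Moving g from 46% to 70% changes these entries by less than 0.1 point. The figures use a normal approximation, whereas the plan names an exact interval, so the change from the f = 0 row matters more than the second digit.

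**Step 3: what f would have to be.** f is the share randomised before angiography multiplied by the share of those who then lack a qualifying occlusion. The documents give neither. As illustrations, 30% × 10% gives f = 3%, while f = 10% needs something like 50% × 20%.

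**Step 4: the other direction.** Under the plan's own assumption (Envi-SR better by 4.5 points, 135 per arm), the same model lowers power from 79.9% to 78.8% at f = 5% and 77.7–77.8% at f = 10%.

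**The case against.** - **The trial's type I error is unchanged.** A reader might infer that the nominal 2.5% is breached. The documents do not support that: Section 8.2 plans the hypothesis for the ITT population, and for that hypothesis the error stays at 2.5%. The table concerns a different target, the effect in subjects with a qualifying occlusion. This objection stands, and the point is limited accordingly.
- **f is probably small.** Angiography first is the stated preference in Section 6.8.2.5 and the rule in Section 6.8.2.7. Nothing supports a share of 10% or more, and the documents give no figure for IV t-PA use in this trial. This stands as to size.
- **Criterion 7 is not wholly unchecked.** Section 1.1.2 describes CTA or MR for confirming large-vessel occlusion, and in Section 6.3 the Core Lab confirms occlusion on baseline CTA/MRA. Location can therefore be screened without a catheter. Only the eTICI grade and the angiographic confirmation clearly need the run. This stands.
- **Zero device effect is the extreme case.** Section 6.8.2.8 speaks of ITT membership whatever the treatment. A subject who fails on grade or site may still be treated with the assigned device, so the table gives upper bounds for each f. This stands.
- **Unblinding does less damage than it may seem.** The investigator learns the arm only at randomisation (Section 3.6), and the occlusion-site stratum has to be known to obtain the assignment. Knowledge of the arm therefore cannot alter that value. Per-protocol eligibility need not rest on the operator either, because the Core Lab reads the lesions (Section 6.9) and works blinded to site assessments and clinical information for the angiographic endpoints (Section 3.6.3).
- **A restricted analysis may exist elsewhere.** Section 8 defers detail to a SAP whose separate text is not in the document reviewed, so this cannot be excluded.

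None of these removes the contradiction between Sections 6.8.2.5 and 6.8.2.7, or the retention in ITT of subjects who lack a qualifying occlusion.

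**Conclusion.** The concern holds in a limited form. The plan contradicts itself on whether angiographic eligibility is settled before assignment. Following Section 6.8.2.5 can put subjects without a qualifying occlusion into the primary analysis set. If Envi-SR is truly 12.5 points worse where an occlusion exists, the chance of passing it as non-inferior rises above 2.5%. For an assumed f of 1–5% the chance is about 2.6–3.2% at 135 per arm and 2.7–3.4% at 224 per arm. At an assumed 10% it is 4.0% and 4.5–4.6%. These figures rest on an f that the documents do not supply and on no device effect in that share.

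Two stronger readings are not supported. One is that the ITT test itself is invalid. The other is that dilution always favours the sponsor: if Envi-SR is better, it costs up to about two points of power at f = 10%.

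The follow-up statements also need reconciling. A reader might set the 24 hours in Section 12.4.1 only against Section 6.8.2.8. It conflicts at least as directly with the 48 hours in Sections 5.3 and 6.8.2.6, because Section 5.1.1.1 defines enrolled screen failures as not randomised. Severity: should-fix.

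**What to change.** 1. Reconcile Section 6.8.2.5 with Section 6.8.2.7 and criterion 7 by deleting the sentence that accepts later angiography. Make eTICI grade and occlusion site required entries in the web system before an assignment is released. Angiographic failures then become pre-randomisation screen failures under Section 6.8.2.6.
2. Keep any subject already randomised before angiography in ITT with full 90-day follow-up, and report the number affected by arm.
3. Pre-specify a sensitivity analysis of the primary endpoint in subjects whose baseline occlusion is confirmed by the Core Lab, and state that this reading is made without knowledge of the arm.
4. Reconcile the follow-up statements in Sections 5.3, 6.8.2.6, 6.8.2.8 and 12.4.1.

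**Cost.** The change needs protocol wording and an edit to the randomisation form. Section 6.8.3 already uses angiography to locate the occlusion in every procedure, but assignment would come slightly later in the case. Angiographic failures would still count towards the 560-consent cap, now as screen failures and not as ITT subjects. The cap leaves 560 − 448 = 112 places for screen failures, which is 25% of 448 and 20% of 560. Replacing a share f of 448 needs 448/(1−f) − 448 further consents before other screen failures: about 5 at f = 1%, 24 at 5% and 50 at 10%. The 25% allowance in the Maximum Sample Size paragraph of Section 8.2 should be checked against this.

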#### **6.8.2.6. Screen Failure Prior to Randomization – Follow-up**

Subjects that have been enrolled (i.e., consented) but not randomized will be followed for a minimum of 48 hours or until discharge, whichever is earlier, to monitor subject safety. The reason for screen failure and follow-up will be captured in the *Early Exit Due to Screen Failure* eCRF.

#### **6.8.2.7. Randomization method**

Subjects meeting the enrollment criteria, including angiographic criteria, will be randomly assigned to a treatment group in a 1:1 ratio, Envi™-SR to Control device. Randomization will define the ITT population and the assignment will determine the treatment group for the ITT analysis. Randomization assignments will be allocated through an electronic system, each initiated study site will be issued their own unique password, at least one password per site, and multiple passwords will be assigned if more than one person is randomizing subjects. Thus, Investigators can quickly determine the randomization assignment and the treatment assignment will be documented for monitoring. Deviations in treatment from the randomized

assignment will be recorded in the *Protocol Deviation* eCRF as a protocol deviation.

#### **6.8.2.8. Screen Failure After Randomization – Follow-up**

Subjects that have been enrolled and randomized but subsequently are found to not meet inclusion / exclusion criteria will be recorded in the Deviation eCRF as a protocol deviation. These subjects are a part of the ITT population regardless of treatment and will be followed per standard study procedures.

#### **6.8.3. Procedure**

- Using standard interventional techniques access the arterial system and using angiography, determine the location of the occluded vessel.
- Using standard angiographic technique, navigate a compatible guide / intermediate catheter, then navigate a compatible microcatheter and guidewire to the thrombus location.
  - It is recommended to use the Retriever with a proximal flow regulation device, such as a balloon guide catheter.
  - If a distal guide / intermediate catheter is planned to be used, it is recommended to use a balloon guide catheter or long sheath for support. These can also facilitate clot retrieval if the clot and Retriever cannot be pulled into a distal guide / intermediate catheter.
- Advance an appropriate Guide Catheter, Sheath or Balloon Guide Catheter as close to the occlusion as possible. Connect a rotating hemostasis valve (RHV) to the proximal end of this catheter and connect to a continuous flush system.
- Select an appropriate microcatheter. Connect an RHV to the proximal end of the microcatheter and connect to a continuous flush system.
- With the aid of a suitable guidewire, if needed, and using standard catheterization techniques and fluoroscopic guidance, advance the microcatheter up to and across the occlusion so that the distal end of the microcatheter is positioned distal of the occlusion.
- Remove the guidewire from the microcatheter and, if desired, gently infuse contrast media through the microcatheter to visualize the distal end of the occlusion.
- Select the appropriate Envi™-SR or Control Device based on target vessel anatomy. Follow Instructions for Use provided in device packaging for positioning, deployment and retrieval and cleaning and re-use of device.
- Do not attempt more than three (3) retrieval attempts with assigned device in the same vessel.
- Note: Direct aspiration prior to 3 passes with randomized device is not allowed per protocol unless there is a valid exception per Section 3.5.

